The purpose of this study is to evaluate the following hypotheses in a population of CHD patients with elevated symptoms of anxiety. The present study will examine the impact of a 3-month intervention of exercise, Lexapro, or placebo on anxiety symptoms and CHD biomarkers among individuals with cardiac disease and elevated anxiety. We hypothesize the following: (1) Both exercise training and medication will reduce anxiety symptoms to a greater extent than placebo; (2) Exercise training will improve CHD biomarkers of risk including autonomic regulation, vascular endothelial function, and inflammation more than either medication or placebo; and (3) Improvements in CHD biomarkers will be mediated by reductions in symptoms of anxiety. We also will explore potential moderators of treatment (e.g., anxiety diagnoses, CHD severity) as well as the longer-term benefits of treatment by documenting medical events and health care costs over a follow-up period of up to 4 years.

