Treatment of Anxiety Disorders in Cardiac Patients. Despite compelling reasons for treating anxiety in CHD patients, there have been few trials that have examined the effects of treating anxiety symptoms in cardiac patients, and no studies reported the effects of treating anxiety on clinical outcomes. Several studies, including the ENRICH trial, have examined the effects of treating depressed post-MI patients,[35] and several pharmacologic studies have examined the effects of SSRIs on depressive symptoms and outcomes in cardiac patients.[36-40] The SADHART-CHF trial found no advantage for sertraline over placebo in either reducing depression or in improving clinical outcomes.[40] The SADHART study[36] also reported no differences between CHD patients receiving sertraline compared to placebo, although greater reductions in depressive symptoms were observed in the subset of patients with more severe depression. We will consider more severe anxiety (i.e., diagnosed anxiety disorders) as a potential moderator of treatment in our proposed RCT.

Exercise and Anxiety. The use of aerobic exercise has been widely used in many secondary prevention programs[41] and may reduce risk of fatal CHD events.[42] The mechanisms for this benefit remain uncertain, although exercise has been shown to reduce traditional risk factors, such as hypertension and hyperlipidemia,[41] attenuate cardiovascular responses to mental stress and reduce myocardial ischemia,[43-46] and reduce depressive symptoms in patients with MDD,[47] heart failure,[48] and in CHD patients with elevated depressive symptoms.[49] Epidemiological studies have observed an inverse relationship between exercise and anxiety. In a study of 8,098 adults, Goodwin[50] reported that persons who indicated that they exercise “regularly” were at reduced risk for being diagnosed with an anxiety disorder compared to their sedentary counterparts. There have been many exercise trials that have reported anxiety as an outcome.

For example, Wipfli and colleagues[51] found that exercise was associated with an overall effect size of 0.48, indicating greater reductions in anxiety symptoms compared to no-treatment controls, and Herring

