## **9. Study Interventions:**

**Randomization:** All eligible subjects will be randomly assigned to one of the 3 treatment conditions. Randomization will occur after each subject has completed the assessment protocol and will adhere to standard procedures for randomized clinical trials.[162] We will employ a conditional randomization procedure wherein equal proportion of participants with anxiety disorders will be assigned to the respective treatment groups. We also will stratify by gender (male/female), history of myocardial infarction (yes/no), and age (<60/≥60). Our anticipated sample size is 150 patients, wherein randomization will include 60 patients to Exercise Training, 60 patients to Medication, and 30 patients to Placebo. We anticipate needing to consent 300 patients in order to reach our sample size goal.

**1. Supervised aerobic exercise.** Patients will exercise three times per week, under medical supervision, at a level of 70-85% of their  $VO_{2peak}$  as determined at the time of their baseline exercise treadmill test. Patients' exercise will consist of 10 minutes of gradual warm-up exercises followed by 35 minutes of continuous walking, biking, or jogging, and 5 minutes of cool down exercises for a total a 50 minutes per session. Patients will be instructed to monitor their radial pulses and will be checked at least three times per session to ensure that they are within their prescribed exercise training ranges. Weekly supervised exercise sessions may take place at one of four sites chosen by the patient: Duke Cardiopulmonary Rehabilitation at Croasdaile, WakeMed Health and Hospitals, UNC Wellness Center at Meadowmont, and Alamance Regional Medical Center. Although depending on the geographic location of participants, other sites may be recruited for participation.

At UNC Wellness Center at Meadowmont, [name] will oversee recruitment and exercise interventions, provide active consultation and collaboration in all aspects of the study, and contribute to data analysis and manuscript writing, while [name] will assist with recruitment and oversee participation of subjects. Both investigators will have access to Duke PHI. At WakeMed, [name] and staff will work in their normal capacity to supervise patient exercise. At Alamance Regional Hospital, now owned by Cone Health, [name] will work in her normal capacity to supervise patient exercise.

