## **12. Data Management and Statistical Considerations**

**Data Analytic Approach.** The basic analytic strategy is a linear model carried out in the MPlus modeling software,[164] with treatment group contrasts as factors, and ethnicity, age, gender, and pre-treatment measure of the outcome variable as the adjustment covariables. The intent-to-treat principle (ITT) will be followed in all models, using full information maximum likelihood available in MPlus to manage missing data. For the case of the primary outcome, HADS-A, the model will include post-treatment HADS-A score as the response, with the predictors including two planned contrast variables representing 1) the two active treatments (exercise and escitalopram) vs. placebo and 2) exercise vs. escitalopram, with ethnicity, gender, age, and pre-treatment level of the HADS-A as the adjustment covariables. The contrast tests among treatment groups will be examined directly, i.e., no omnibus or “gateway” test will be required before interpreting them. In support of the HADS-A outcome, we also will compare the pattern of weekly changes in the STAI scores over time using a repeated measures model with Proc Mixed in SAS (SAS Institute, Cary, NC). The primary biomarker outcome, HRV, will be evaluated similarly. It is possible that a small number of participants may require off-protocol psychotropic medication during the course of the trial. These participants will be included in the ITT analysis and will not be replaced. We also will perform a sensitivity analysis with change in medication included as an adjustment variable in the statistical model. Finally, we will compare the treatments on the number of clinical events using a generalized linear model with the appropriate distributional form (e.g., negative binomial), using the same contrasts and covariates as in the linear model described above.

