In addition to treatment effects, we also will test the hypothesis that pre- to post-treatment change in HADS-A scores will mediate the improvements in intermediate CHD biomarkers. M-Plus allows a direct, formal test of this hypothesis via path analysis modeling. For example, a model will be specified so that both active treatment groups will be contrasted against the placebo arm, with a variable representing the change in anxiety intervening between the treatment contrast variables and post-treatment HRV (with the covariates, pre-treatment HRV, age, ethnicity, and gender). Mediation is tested by examining the product of the two component path coefficients (treatment → mediator → outcome) and its standard error, which yields the point estimate of the mediated effect along with the statistical significance of treatment on post-treatment biomarker (e.g., HRV) via change in HADS-A.[165] We also will explore possible treatment-specific mediators (e.g., change in VO2 mediating change in HRV for the Exercise group). In addition to the above tests, we will examine the impact of dropout on the estimates

of treatment effects using mixture modeling available in MPlus. Specifically, we will examine the primary outcomes using Rubin's Complier-Average Causal Effect Estimation (CACE) model,[166] which estimates the effect of treatment for all participants who adhere to the protocol irrespective of treatment group assignment. We will explore possible moderators of the treatment effect using interaction terms. Specifically, we will examine the possible moderating effects of gender, race, patient expectations, and initial severity of anxiety (e.g., DSM-5 diagnosis for an anxiety disorder); if sufficient numbers, we also plan to explore individual diagnoses by adding treatment interaction terms for these variables simultaneously with the primary model, and using a pooled test of the terms to determine whether the individual terms should be interpreted. Participants who voluntarily drop out of treatment or who are unable to complete our protocol will not be replaced but will undergo follow-up assessment.

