**Power Analysis.** Our study is powered with a focus on the primary hypothesis test: the treatment effect on anxiety as measured by HADS-A scores. We estimated power and sample size under the following assumptions: an alpha of .05, a linear model with age, gender, ethnicity, and baseline HADS-A score as covariates, a conservative estimate of the R-squared of .20 for the full model predicting post-treatment HADS-A, a 15% attrition rate, and two planned contrasts: active treatment vs. placebo and exercise vs. escitalopram. The comparison of primary interest will be active treatments vs. placebo. We estimate that a sample size of 150 (127 after attrition) will yield .80 power to detect at least a .45 SD difference between the active treatments and Placebo. In the general linear model, the exercise vs. escitalopram test will be only slightly less powered in being able to detect a .50 SD difference. In response to a previous reviewer comment, we believe that achieving this effect size is feasible. For example, in individuals with high anxiety sensitivity, Broman-Fulks[167] reported a .61 SD difference between exercisers and controls. We also re-examined data from a subset of highly anxious patients ( $STAI \geq 45$ ;  $N=32$ ) participating in our recently completed UPBEAT study[49] and found an effect size of .85 SDs on the STAI for both active treatments vs. placebo controls. We note that our power estimates are conservative in that the R-squared for the model is likely to be greater than .20 and dropout may be lower than 15%. With respect to the secondary outcome of HRV, our prior work showed that the R-squared between the baseline covariates and HRV was .73, greatly increasing the power of the tests of treatment on HRV. For the test of exercise vs. escitalopram on HRV, our primary CHD biomarker of interest, we will have a power of .80 to detect a .25 SD effect at alpha of .05. Finally, for our ancillary outcomes, including FMD, lipids, urinary catecholamines, and inflammatory markers, we have sufficient pilot data for FMD, which we use as an exemplar for power estimates: our earlier work showed that for FMD, the multiple R-squared between the baseline covariates (age, gender, ethnicity, and baseline FMD) and FMD was .50. Thus, we will have a power of .80 to detect a .34 SD effect for FMD with an alpha of .05. We estimate the power for the secondary analysis of treatment on time-to-clinical-event, assuming an event rate of 50% in the placebo group (based on unpublished data from our prior work[49]), 42 months for patient accrual, median follow-up time of 30 months and alpha = .05, is .80 to detect a reduction in event rate of 50% between both treatment groups and placebo, as well as .80 to detect a reduction in event rate of 56% between either intervention group individually and placebo. Unpublished data from our recently completed ENHANCED trial[168] revealed a 54% reduction in major adverse cardiac events among patients participating in CR compared to a matched control group of patients who did not participate in exercise-based CR.

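### The HADS-A and biomarker models omit two of the four factors used to balance randomisation, which may give up as much as about 4 points of power

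*Combined protocol and SAP*

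**What the plan says.** Section 9 (Randomization) sets out a "conditional randomization procedure wherein equal proportion of participants with anxiety disorders will be assigned to the respective treatment groups". It continues: "We also will stratify by gender (male/female), history of myocardial infarction (yes/no), and age", with age cut at 60. Allocation is therefore balanced on four binary factors.

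Section 12 (Data Analytic Approach) fits post-treatment HADS-A on two treatment contrasts, "with ethnicity, gender, age, and pre-treatment level of the HADS-A as the adjustment covariables". HRV is handled in the same way, and the remaining biomarkers use the same modelling approach. The HRV path model is specified "with the covariates, pre-treatment HRV, age, ethnicity, and gender". The Power Analysis assumes "a linear model with age, gender, ethnicity, and baseline HADS-A score as covariates".

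Gender and age, two of the four balancing factors, are therefore in every model. MI history is in none. Anxiety diagnosis appears only among the exploratory moderators. Nothing in the document says that the analysis will account for all the balancing factors, or why two are left out.

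**The concern.** Balancing the arms on a factor that predicts the outcome makes the treatment estimate less variable. A linear model that omits the factor leaves its variance in the residual, so the reported standard error does not reflect the gain in balance. The estimate stays unbiased, but the test rejects less often than its nominal 5% under the null and loses power under the alternative. If the factor predicts nothing, there is no such effect.

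The documents support prognostic value unevenly.

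- **HADS-A.** Section 3 treats diagnosis as a severity marker: "We will consider more severe anxiety (i.e., diagnosed anxiety disorders) as a potential moderator of treatment". Baseline HADS-A will already absorb part of that. The documents give no reason why MI history should predict HADS-A.
- **HRV.** Section 2 lists CHD severity among possible moderators. Reading MI history as part of CHD severity is an inference. The Power Analysis reports that the "R-squared between the baseline covariates and HRV was .73", which leaves little for either factor to add.

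Efficiency matters here because the comparison of primary interest rests on a small placebo arm: 30 × .85 = 25.5 expected completers.

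**Working it through.** **Inputs from the documents.** N = 150, allocated 60:60:30 (Section 9); 15% attrition, alpha .05, R-squared .20 for HADS-A and .73 for HRV, and an effect of .45 SD for active treatment against placebo (Section 12, Power Analysis).

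**Assumptions.** Two-sided testing, 16 crossed strata (2 × 2 × 2 × 2), permuted blocks of 5, factor prevalences of 50%, outcomes missing at random, and r, the share of residual variance that the two omitted factors explain beyond the planned covariates.

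**1. The plan's own figure.** The stated power for .45 SD is .80. With 127 completers split 25.4 to 101.6, SE = √(.80 × (1/25.4 + 1/101.6)) = .198. Then .45/.198 = 2.27, and power = Φ(2.27 − 1.96) = .62. The stated .80 does not come back from the 60:60:30 allocation. That is a separate matter, and the comparison below starts from about .61 to .62. The .50 SD contrast of exercise with escitalopram does reproduce, at .80.

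**2. Closed form under perfect balance.** Let c = .45/.198 = 2.27.

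- Level of the planned test: 2Φ(−1.96/√(1 − r))
- Power of the planned test: Φ((c − 1.96)/√(1 − r))
- Power of the adjusted test: Φ(c/√(1 − r) − 1.96)

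| r | Level, planned | Power, planned | Power, adjusted |
|---|---|---|---|
| .02 | .048 | .622 | .630 |
| .05 | .044 | .624 | .643 |
| .10 | .039 | .627 | .667 |

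**3. Simulation with blocking and dropout** (16,000 runs per cell).

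| r | Mean reported SE, planned → adjusted | True SD of estimate, planned → adjusted | Power, planned → adjusted | Level, planned |
|---|---|---|---|---|
| 0 | .2005 → .2009 (+0.2%) | .2006 → .2012 | .609 → .607 | about .05 |
| .02 | .2005 → .1989 (−0.8%) | .1992 → .1992 | .609 → .615 | .048 |
| .05 | .2006 → .1959 (−2.3%) | .1969 → .1961 | .608 → .629 | .044 |
| .10 | .2006 → .1906 (−5.0%) | .1932 → .1909 | .612 → .651 | .041 |

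At r = .10 the planned model overstates the standard error by .2006/.1932 − 1 = 3.8%. Most of the gain comes from correcting that overstatement: the true SD falls by only 1.2%. Separate runs of the same design gave .606 → .622 at r = .05 and .606 → .645 at r = .10. With blocking on anxiety disorder alone, the power changes are −0.6, +0.2, +1.2 and +3.5 points at r = 0, .02, .05 and .10.

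**4. Other contrasts, closed form.** For exercise against escitalopram on HADS-A at .50 SD, power goes from .811 to .824 (r = .05) and from .817 to .844 (r = .10). For the same contrast on HRV at .25 SD, it goes from .683 to .701 and from .688 to .724. For HRV, r = .10 is .10 × .27 = 2.7% of total variance; for HADS-A it is .10 × .80 = 8%.

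**5. Event model.** Section 12 carries the linear model's covariates into the model for clinical events. A negative binomial simulation assumed .75 events per placebo patient (30% a year × 2.5 years), dispersion .5, no dropout and an MI rate ratio of 1, 1.5 or 2. At a treatment rate ratio of .5, adding MI history moved power from .629 to .630, .631 to .639 and .613 to .630 (Monte Carlo SE .011). The adjusted test's level was .051, .058 and .061, against .049, .052 and .051 unadjusted. No gain is claimed there.

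**The case against.** The strongest reply is that a few points is the top of an assumed range. With a 50% prevalence factor and residual variance .80, explaining a share r requires a difference of 2√(.80r) between patients with and without the factor, after adjustment for baseline HADS-A. That is .25 SD at r = .02, .40 SD at r = .05 and .57 SD at r = .10. The last exceeds the .45 SD treatment effect that the trial is designed to detect. This stands: gains near 4 points need a strong factor, and the gain could be under 1 point.

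The case for MI history in the HADS-A model is also weak, since nothing in the documents links the two. That stands as a comment on expected gain. The argument for including it is that the trial randomises by it and that it costs one degree of freedom.

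Conservatism also depends on balance being achieved. Block size and the mechanics of the conditional randomisation are not described, and 150 patients over 16 cells is about 9 per cell. Under simple randomisation at r = .10 the planned test's level is about .049, so the conservatism largely goes. The power gain from adjusting, about 3.5 points, remains.

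Finally, the absence of bias applies to the randomised contrasts only. In the path model, the link from HADS-A change to HRV is not randomised. If diagnosis predicts both, leaving it out could confound that link, and the power figures above do not describe it. This is a limit on the calculation and a further reason to add the terms there.

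**Conclusion.** The concern holds as a point of efficiency. Two of the four balancing factors are missing from the HADS-A and biomarker models without explanation. Conclusions about treatment from the planned models remain valid. Adding the factors changes power by between a loss of about half a point and a gain of about 4 points over r = 0 to .10, and by about 2 points at r = .05. The planned test's level falls from .05 to about .04 at the top of that range. Both results depend on a prognostic strength that the documents do not give; the size of the conservatism also depends on the assumed blocking. The change does not repair the separate gap between the stated .80 power and the roughly .62 that follows from the allocation.

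**What to change.** Add anxiety-disorder status (yes/no, as used at randomisation) and MI history (yes/no) to the prespecified covariates of the primary HADS-A model and of the biomarker linear models, including the HRV path model. Keep age, gender, ethnicity and the baseline value of the outcome. State explicitly whether the two terms also enter the clinical event model, which otherwise inherits them by cross-reference.

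The cost is one line in Section 12. Both variables are known for every patient at randomisation. The model uses two more of about 120 residual degrees of freedom (127 completers less 7 parameters: intercept, two contrasts and four covariates). If neither factor is prognostic, the simulated loss is 0.2 to 0.6 points of power. The terms should be fixed before unblinding, because adding them later would look selective.

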#### V. Post-treatment Assessments at 3-Months and at 9-Months (Six-month follow-up)

At the conclusion of the 3-month intervention (post-treatment), or at the time a participant may drop out of the study (or in the rare instance of requiring additional or different anxiolytic treatment outside of our protocol), patients will complete the same clinical, biomarker, and psychometric test battery that they completed at baseline. At the 6-month follow-up, we will assess anxiety, patients' exercise habits, any psychiatric treatment, psychopharmacologic medications, aerobic fitness using a 6-minute walk test, and cardiac status, including revascularization procedures and CHD events. This will be a naturalistic follow-up that we have used in previous trials,[157, 158] which will allow us to determine patients' anxiety status 6 months after the conclusion of study-related treatment, along with changes in health habits and measures of quality of life. Figure 2 presents an expanded view of the assessment schedule and design of the study. For clinical events, we carefully will document cardiac-related hospitalizations and

emergency room visits, revascularizations, and any deaths for up to 4 years post-treatment.

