Patients will see [name] (who will be blinded to pill condition) at week 0 (baseline), week 1, week 2, week 4, week 8, and week 12 with phone consultations at weeks 3 and 6. Patients will be contacted weekly by telephone between regularly scheduled visits to take the STAI-State. [name] will make all medication adjustments based primarily upon STAI scores and safety/tolerability/side-effect assessments. Patients will be randomly assigned to receive escitalopram (5 mg/d) or placebo. Depending on symptoms, daily escitalopram (or placebo) doses will be titrated to 10 mg after week 2 and to 15 mg or placebo equivalent at week 3 if patients show no change or only minimal improvement. At week 4, if patients show no change or only minimal improvement, they will receive up to a maximum daily dose of 20 mg or placebo equivalent. The dose can be reduced in the event of side effects. [name] is an experienced clinical investigator in pharmacological RCTs and will serve as the treating psychiatrist for this trial. In all cases, the treating physician will use supportive measures to help manage medication side effects. In cases of severe side effects or patient discomfort, the physician may elect to decrease the medication dosage at any time or permit unscheduled visits during the study. At each medication dispensing visit, the patient will see the treating physician, who will prescribe the medication, and the study coordinator, who will order the medication, which will be signed off by the treating physician. The signed order will be released to and filled by the on-site investigational pharmacy. The pharmacy will dispense enough medication to last to the next expected dispensing visit plus a 5-day window. Patients will be instructed to use their previous bottle of medication before opening and using the newest provided bottle(s). The pharmacy will be responsible for medication storage and verifying expiration, maintaining the blind, storing codes in a sealed envelope accessible at emergencies, and for dispensing medication.

Patients and raters will be kept blinded to drug therapy assignments both during the treatment phase (3 months) and until the patient has completed the post-treatment assessments. [name], who will perform the ongoing medication monitoring and safety ratings, will be blinded until the completion of the trial. Limited use of sleep medications, but not other anxiolytic agents, will be permitted (see Human Subjects).

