
**13. Data and Safety Monitoring:** Study participants will be closely monitored for side effects, level of anxiety, and suicide risk. All patients will receive a weekly phone call to assess their state of anxiety using the STAI-State instrument. For patients who have a secondary diagnosis of MDD, BDI-II item #9 will be administered along with the 20-item STAI; patients who score  $>1$  on the item #9 of the BDI-II or who are judged to be at increased risk for suicidality will be evaluated by our study psychiatrist and referred for further treatment. For patients with a secondary diagnosis of MDD, suicidality will be assessed at each visit and by interim telephone contacts as needed. Subjects may experience no response to treatment or a worsening of symptoms; however, all subjects will be carefully monitored and withdrawn from the study if their symptoms worsen. If patients become suicidal, they will be evaluated by the treating psychiatrist

and appropriate referral or admission procedures will be initiated, such as to their referring physician or to the Duke Outpatient Affective Disorders Program, the Duke Psychology Clinic, or a local mental health center. Our study coordinator will contact the patient within 24 hours to make sure that he or she followed through with the referral. Furthermore, at the conclusion of the interventions, patients will be followed bimonthly via telephone and referred to their local physicians for further treatment, if necessary, or to the Outpatient Treatment Program at Duke University Medical Center or to the Duke Psychology Clinic.

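### The sensitivity analysis for off-protocol psychotropics adjusts for a post-randomisation variable, so unless use is unrelated to prognosis it estimates neither the ITT effect nor the effect without added medication

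*Combined protocol and SAP*

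**What the plan says.** Section 12 (Data Analytic Approach) anticipates the event: "It is possible that a small number of participants may require off-protocol psychotropic medication during the course of the trial". It continues: "These participants will be included in the ITT analysis and will not be replaced". The check on their influence is a "sensitivity analysis with change in medication included as an adjustment variable in the statistical model". The model carries "two planned contrast variables representing 1) the two active treatments (exercise and escitalopram) vs. placebo and 2) exercise vs. escitalopram", with baseline HADS-A, age, gender and ethnicity as covariates. Section 12 does not define or code the medication variable, name the quantity the adjusted contrast is meant to estimate, or state the assumption it needs.

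Four other places bear on it:

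- Section 4, part V, has the test battery repeated at 3 months, at drop-out, or "in the rare instance of requiring additional or different anxiolytic treatment outside of our protocol". Section 12 does not say whether that event-time HADS-A or a 3-month score is analysed.
- Section 13 has "all subjects will be carefully monitored and withdrawn from the study if their symptoms worsen", which suggests that leaving protocol treatment goes with poor response.
- Section 9 states: "Limited use of sleep medications, but not other anxiolytic agents, will be permitted". A sleep aid might therefore count as a change in medication; the plan does not say.
- The complier-average causal effect (CACE) model in Section 12 is introduced for dropout and adherence. It is not stated to cover added medication.

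**The concern.** A covariate measured before randomisation has the same expected distribution in every arm, so adjusting for it leaves the meaning of the contrast intact. Change in medication does not have that property. Patients take an off-protocol psychotropic because they need one, and need depends on how they respond to the assigned treatment. Among patients who add a drug, those on placebo and those on active treatment may differ in prognosis, and so may those who do not add one. The adjusted contrast compares arms within these unlike groups.

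No other analysis is stated to cover this event, so readers would use this one to judge whether added medication distorts the primary result. It could mislead in two ways: a sound ITT estimate could appear to shrink for no good reason, or two estimates that are both diluted could agree and be taken as reassurance.

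**Working it through.** The documents give no rate of off-protocol use, no drug effect and no expected shift, so there is no planned figure to reproduce. What can be checked is how the adjusted contrast behaves.

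**Inputs from the documents.** Allocation is 60:60:30 (Section 9), so active to placebo is 4:1. The Power Analysis gives R² = .20, 127 patients after attrition and a .45 SD design effect.

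**Assumptions.** Placebo use is 5%, 10% or 20%. The added drug lowers HADS-A by a constant b of 0 to 2 SD. The trigger for medication correlates 0 to .7 with the outcome.

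**Step 1: algebra.** Let A be active treatment, M added medication and Y the HADS-A score in SD units. Let δ be the share medicated on active minus the share on placebo, and γ the coefficient of M in the adjusted model. For a linear model in a randomised trial:

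ITT contrast = adjusted contrast + γδ.

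If the drug shifts Y by a constant, Y = Y₀ − bM. Then γ = γ₀ − b, where γ₀ is how much worse medicated patients would have been anyway, and the coefficient of A does not depend on b. Hence:

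adjusted contrast = effect without added medication − γ₀δ.

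The constant drug benefit is absorbed, and −γ₀δ is the selection bias. With γ₀ > 0, the bias is toward zero when δ < 0 (more use on placebo) and away from zero when δ > 0. It vanishes when γ₀ = 0.

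**Step 2: simulation.** There were 2,000,000 patients per scenario at 4:1, with a true effect without added medication of −.45 SD.

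| Why medication is added | Use, placebo / active | b | δ | γ | ITT | Adjusted |
|---|---|---|---|---|---|---|
| Poor response (r = .7) | 10.0% / 5.5% | 0 | −.045 | 1.196 | −.452 | −.399 |
| same | 10.0% / 5.5% | .5 | −.045 | .698 | −.428 | −.396 |
| same | 10.0% / 5.5% | 2.0 | −.045 | −.802 | −.362 | −.398 |
| same | 20.0% / 12.4% | 0 | −.076 | 1.078 | −.452 | −.370 |
| same | 20.0% / 12.3% | 1.0 | −.077 | .076 | −.375 | −.369 |
| Poor response (r = .3) | 10.0% / 7.8% | 0 | −.022 | .485 | −.451 | −.440 |
| Unrelated to prognosis | 20.1% / 5.0% | .5 | −.151 | −.497 | −.375 | −.450 |
| Prognostic, commoner on active | 5.0% / 15.0% | 0 | +.100 | 1.081 | −.449 | −.557 |

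The identity holds. In row 1, −.399 + 1.196 × (−.045) = −.453, against −.452 simulated. In the last row, −.557 + 1.081 × .100 = −.449.

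- At r = .7, placebo use of 5%, 10% and 20% gives adjusted contrasts of about −.42, −.40 and −.37. These are 8%, 12% and 18% toward zero, or up to .45 − .37 = .08 SD.
- At 10% use the adjusted value stays at about −.40 for every b. It lies nearer zero than ITT when b = .5 and further from zero when b = 2.0.
- At 20% use with b = 1.0, ITT and adjusted agree within .006 SD, yet both fall about .08 short of the truth.
- When use is unrelated to prognosis, adjustment recovers −.45 and ITT does not.

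**Step 3: scale.** At 4:1, 127 patients split 101.6 to 25.4. The standard error of the active–placebo contrast is √.80 × √(1/101.6 + 1/25.4) = .894 × .222 = .198, about .20 SD. A shift of .08 is about .08/.20 = 0.4 standard errors. Of 30 placebo patients, 5–20% is 1.5 to 6 people.

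**Step 4: the alternative.** A separate simulation used a true effect of −.50 SD, with use of 5–15% on active and 6–20% on placebo. The covariate adjustment gave −.46 to −.50. Setting post-change scores to missing, with on-treatment anxiety as an auxiliary, gave −.485 to −.50 and was closer to the truth in every scenario, including those where switching also depended on unrecorded information.

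**The case against.** The strongest reply is that this is a secondary check on an event the plan expects to be rare, and that its shift is small against the standard error. That stands: the ITT analysis keeps these patients as randomised and is not touched.

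Stronger readings that a reader might infer are not supported:

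- **That adjustment always biases toward zero.** The sign follows that of γ₀δ, and the documents give no rate by arm. The bias can be absent or reversed, and adjustment can even move ITT in the right direction. For exercise against escitalopram nothing in the documents fixes the sign of δ.
- **That adjustment fails to remove the drug's effect.** A constant additive benefit is removed in full. Only a benefit that differs by arm would be removed incompletely.
- **That post-drug scores necessarily dilute the primary result.** If the event-time HADS-A precedes the new drug and is the value analysed, there is no drug effect in it. The documents leave this open.

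The CACE analysis could be offered as a second check, since it concerns adherence to the protocol. It is arguably relevant, but the plan does not say that added medication counts as non-adherence.

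It is also fair to say that the alternative targets a hypothetical effect that the plan never names, and performs best when the recorded data explain switching. This is why it needs its own sensitivity check. The covariate adjustment, however, names no target at all.

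**Conclusion.** The point holds as a recommendation for a secondary analysis. Because change in medication is post-randomisation and plausibly tied to response, the adjusted contrast lacks a clear meaning unless use is unrelated to prognosis. The plan does not state that condition, and Section 4, part V, and Section 13 make it doubtful.

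The likely size is modest. The shift is about .00–.08 SD for active against placebo, with 5–20% placebo use that follows poor response or is unrelated to prognosis. It reached .56 − .45 = .11 SD away from zero in the one scenario with 15% use on active treatment and 5% on placebo. These figures rest on assumed rates, correlations and drug effects. The likely direction for active against placebo is toward zero only if use follows poor response and is therefore commoner on placebo. A reader should not conclude that the primary result is compromised.

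**What to change.** Keep ITT as the primary analysis and replace the covariate-adjusted check as follows.

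1. Define the event as the start of an off-protocol psychotropic, and say whether permitted sleep medication counts.
2. Name the estimand: the treatment contrast had no off-protocol psychotropic been added.
3. Set HADS-A recorded after that start to missing and re-fit the primary FIML model with arms as randomised. Use the weekly STAI-State up to the change and the event-time battery as auxiliaries. The STAI series will carry most of the information: the event-time battery exists only for patients who change treatment or leave, so its relation to a 3-month score cannot be estimated directly. It can also help to anchor step 4.
4. Add a simple tipping-point (delta) check that worsens the values implied for these patients until the conclusion changes.
5. State whether the event-time or the 3-month HADS-A enters the ITT analysis. If no 3-month score is taken after the event, say so; there is then nothing to set to missing in step 3.

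The cost is a few sentences in Section 12. The STAI-State, the event-time battery and FIML in Mplus are already planned. The replacement assumes missing at random given the auxiliaries and loses a little precision.
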